6.1.4 Response Criteria

6.1.4.1 Evaluation of Target Lesions

Rev. 8/12

Complete Response (CR)

Disappearance of all target lesions. Any pathological lymph nodes (whether target or non-target) must have reduction in short axis to < 10 mm. To be assigned a status of complete response, changes in tumor measurements must be confirmed by a repeat assessment performed no less than four weeks after the criteria for response is met.

Rev. 8/12

Partial Response (PR)

At least a 30% decrease in the sum of the diameters of target lesions, taking as reference the baseline sum diameters. To be assigned a status of partial response, changes in tumor measurements must be confirmed by a repeat assessment performed no less than four weeks after the criteria for response is met.

Progressive Disease (PD)

At least a 20% increase in the sum of the diameters of target lesions, taking as reference the smallest sum on study (this includes the baseline sum if that is the smallest on study). In addition to the relative increase of 20%, the sum must also demonstrate an absolute increase of at least 5 mm. (Note: the appearance of one or more new lesions is also considered progression, See Section [6.1.4.3](#)).

Stable Disease (SD)

Neither sufficient shrinkage to qualify for PR nor sufficient increase to qualify for PD, taking as reference the smallest sum diameters while on study. (Note: a change of 20% or more that does not increase the sum of the diameters by 5 mm or more is coded as stable disease)

To be assigned a status of stable disease, measurements must have met the stable disease criteria at least once after study entry at a minimum interval of 12 weeks.

6.1.4.2 Evaluation of Non-Target Lesions

Complete Response (CR)

Disappearance of all non-target lesions and normalization of tumor marker level. All lymph nodes must be non-pathological in size (< 10 mm short axis)

NOTE: If tumor markers are initially above the upper normal limit, they must normalize for a patient to be considered in complete clinical response.

Non-CR/Non-PD

Persistence of one or more non-target lesion(s) and/or maintenance of tumor marker level above the normal limits.

Progressive Disease (PD)

Appearance of one or more new lesions and/or *unequivocal progression* of existing non-target lesions (see Section 6.1.4.3). *Unequivocal progression* should not normally trump target lesion status. It must be representative of overall disease status change, not a single lesion increase.

When the patient also has measurable disease, there must be an overall level of substantial worsening in non-target disease such that, even in the presence of SD or PR in target disease, the overall tumor burden has increased sufficiently to merit discontinuation of therapy. A modest "increase" in the size of one or more on-target lesions is usually not sufficient to qualify for unequivocal progression status. The designation of overall progression solely on the basis of change in non-target disease in the face of SD or PR of target disease will therefore be extremely rare.

When the patient only has non-measurable disease, the increase in overall disease burden should be comparable in magnitude to the increase that would be required to declare PD for measurable disease: i.e., an increase in tumor burden from "trace" to "large", an increase in nodal disease from "localized" to "widespread", or an increase sufficient to require a change in therapy.

Although a clear progression of "non-target" lesions only is exceptional, the opinion of the treating physician should prevail in such circumstances, and the progression status should be confirmed at a later time by the review panel (or Principal Investigator).

6.1.4.3 Evaluation of New Lesions

The appearance of new lesions constitutes Progressive Disease (PD).

6.1.4.4 Evaluation of Best Overall Response

The best overall response is the best response recorded from the start of the treatment until disease progression/recurrence or non-protocol therapy (taking as reference for progressive disease the smallest measurements recorded since the treatment started). The patient's best response assignment will depend on the achievement of both measurement and confirmation criteria.

For Patients with Measurable Disease (i.e., Target Disease)

Target Lesions	Non-Target Lesions	New Lesions*	Best Overall Response	Remarks
CR	CR	No	CR	
CR	Non-CR/Non-PD***	No	PR	
CR	Not evaluated	No	PR	
PR	Non-PD***/not evaluated	No	PR	
SD	Non-PD***/not evaluated	No	SD	Documented at least once \geq 12 wks. from study entry
PD	Any	Yes or No	PD	No prior SD, PR or CR
Any	PD**	Yes or No	PD***	
Any	Any	Yes	PD	

* See RECIST 1.1 manuscript for further details on what is evidence of a new lesion.

** In exceptional circumstances, unequivocal progression in non-target lesions may be accepted as disease progression.

***PD in non-target lesions should not normally trump target lesion status. It must be representative of overall disease status change, not a single lesion increase. Please refer to the Evaluation of Non-Target Lesions-Progressive Disease section for further explanation.

NOTE: Patients with a global deterioration of health status requiring discontinuation of treatment without objective evidence of disease progression at that time should be reported as "*symptomatic deterioration*." Every effort should be made to document the objective progression even after discontinuation of treatment.

For Patients with Only Non-Measurable Disease (i.e., Non-Target Disease)

Non-Target Lesions	New Lesions	Overall Response
CR	No	CR
Non-CR/non-PD	No	Non-CR/non-PD*
Not all evaluated	No	not evaluated
Unequivocal PD	Yes or No	PD
Any	Yes	PD

* 'Non-CR/non-PD' is preferred over 'stable disease' for non-target disease since SD is increasingly used as an endpoint for assessment of efficacy in some trials so to assign this category when no lesions can be measured is not advised

6.1.5 Duration of Response

Duration of Overall Response

The duration of overall response is measured from the time measurement criteria are met for CR or PR (whichever is first recorded) until the first date that recurrent or progressive disease is objectively documented (taking as reference for progressive disease the smallest measurements recorded since the treatment started).

The duration of overall CR is measured from the time measurement criteria are first met for CR until the first date that progressive disease is objectively documented.

Duration of Stable Disease

Stable disease is measured from the start of the treatment until the criteria for progression are met, taking as reference the smallest measurements recorded since the treatment started, including the baseline measurements.

To be assigned a status of stable disease, measurements must have met the stable disease criteria at least once after study entry at a minimum interval of 12 weeks.

7. Study Parameters

7.1 Therapeutic Parameters

1. Prestudy scans and x-rays used to assess all measurable or non-measurable sites of disease must be done within **4 weeks** prior to registration.
2. Prestudy CBC (with differential and platelet count) should be done \leq **4 weeks** prior to registration.
3. All required prestudy chemistries, as outlined in Section [3](#), should be done \leq **4 weeks** prior to registration.

NOTE: 1 cycle = 28 days

	Pre-Study		End of Cycles 1 and 2 ⁹	End of Cycle 3 ⁹	Every 3 cycles (after cycle 3) ⁹	At discontinuation of treatment ¹⁰	Post treatment up to 5 years from study entry
	\leq 4 weeks prior to registration	\leq 2 weeks prior to registration					
Height	X						
History, Physical Exam, ECOG PS, Vital signs, Weight	X		X	X	X	X	X ³
Concomitant Medications	X		X	X	X		X ⁸
CBC ¹	X			X	X	X	
Bilirubin, SGOT (AST), SGPT (ALT)	X			X	X	X	
Lipid profile ¹¹	X			X			
HCG ²		X					
Bone scan	X ⁶			X ⁶	X ⁶		X ^{6,8}
Tumor assessment by PE	X			X	X	X	X ⁸
Tumor assessment by CT or MRI ⁷	X			X	X	X	X ⁸
Research blood submissions ⁵	X ⁴			X		X	

- Rev. 8/12
1. CBCs (with differential and platelet count) which includes WBC, ANC, Platelets, Hgb, and Hct.
 2. All females of child-bearing potential must have a blood or urine test within 2 weeks prior to registration to rule out pregnancy.
 3. Every 3 months if patient is $<$ 2 years from study entry, every 6 months if patient is 2-5 years from study entry. No specific requirements if patient is more than 5 years from study entry.
- Rev. 5/11

- Rev. 8/12 4. It is strongly encouraged that the whole blood collected for the genotype verification is collected prior to protocol treatment, but may be collected at the end of cycle three (3) if unable to collect at baseline.
- Rev. 8/12 5. Refer to Sections [7.2](#) and [11](#) for submission instructions.
- Rev. 5/11, 6. Baseline bone scan required in all patients; repeat in follow-up as clinically indicated.
- 8/12 **NOTE:** If bone scan done within 6 months prior to registration showed no evidence suggesting bone metastases and no clinical indication of skeletal pain or other evidence suggesting bone metastases, a repeat baseline bone scan is not required.
- Rev. 5/11, 7. CT or MRI of chest/abdomen/pelvis are required at baseline. Those tests required to follow known site(s) of disease should be repeated at the end of Cycle 3 and then every 3 cycles during treatment and according to the follow up schedule if off treatment, until first progression of disease.
- NOTE: If CT or MRI of chest and/or abdomen/pelvis done within 6 months prior to registration showed no evidence of disease in the area(s) and no clinical indication suggesting new metastases, full re-staging including all areas is not required; however, ensure that disease is evaluable per RECIST requirements (Section [6](#)).
- Rev. 5/11 8. Concomitant medication and tumor assessments are to be done up to (and including) the assessment which shows first progression of disease. If patient discontinues treatment due to reasons other than disease progression, concomitant medication and tumor assessments should be performed until disease progression on the following schedule: Every 3 months if patient is < 2 years from study entry, every 6 months if patient is 2-5 years from study entry. No specific requirements if patient is more than 5 years from study entry.
- Rev. 5/11 9. All tests should be performed at the end of the cycle. A +/- 7 day window will be allowed in case of scheduling problems.
- Rev. 5/11 10. Repeat any test not done within the prior 28 days.
- Rev. 5/11 11. Lipid profile should be fasting.

7.2 Biological Sample Submissions

1. Pathological materials should be submitted for banking as outlined in Section [10](#) per patient consent.
2. Whole blood and plasma must be submitted as outlined in Section [11](#) for CYP2D6 status and tamoxifen and metabolite levels.

NOTE: It is required that biological sample submissions be logged into the ECOG-ACRIN Sample Tracking System (STS) (see Section [10.4](#)) for purposes of monitoring compliance.

NOTE: An informed consent must be signed prior to the use of any samples for any laboratory study or banking.

Rev. 8/12

	Pre-Study ¹	End of Cycle Three (3)	Off-Treatment	Submit to:
Block from Primary Tumor	X			ECOG-ACRIN Central Biorepository and Pathology Facility
Block from Metastatic Site (when available)	X			
Plasma (one (1) 6mL sodium heparin green top tube)*		X	X	
Whole Blood (one (1) 8-10mL EDTA purple top tube - K3)*	X ²			Indiana University School of Medicine

*Mandatory

1. Baseline, prior to treatment.
2. Whole blood is strongly encouraged to be collected at baseline, prior to treatment, but may be collected at the end of cycle three (3) if unable to collect at baseline.

8. Drug Formulation and Procurement

8.1 Tamoxifen

8.1.1 Other Names

Nolvadex, tamoxifen citrate, NSC# 180973

8.1.2 Classification

Hormone antagonist (antiestrogen).

8.1.3 Mode of Action

Tamoxifen and its metabolites possess antiestrogenic activity due to their ability to compete with estradiol for binding to receptors in the cells of tumors that contain high amounts of estrogen receptors (such as breast cancer). The estrogen receptor complex is translocated from the cytoplasm of cancer cells to the nucleus where it reduces DNA synthesis and cellular responses to estrogen. Tamoxifen also displays mild estrogenic activity and induces secretion of transforming growth factor beta (TGF-beta), which has inhibitory effects on many types of epithelial cells.

8.1.4 Storage and Stability

Tamoxifen is stored at room temperature protected from light.

8.1.5 Dose Specifics

20 mg PO daily (as a single dose)

8.1.6 Preparation

Not applicable, tablet is ready for administration.

8.1.7 Route of Administration

Oral.

8.1.8 Incompatibilities

Tamoxifen is a potent inhibitor of hepatic cytochrome P450 mixed function oxidases (MFO). The effect of tamoxifen on the metabolism and excretion of other drugs requiring MFO for activation is unknown. Phenobarbital decreased tamoxifen serum level significantly in one patient. Concomitant bromocriptine therapy has been shown to elevate serum tamoxifen levels. Tamoxifen may potentiate the anticoagulant effects of warfarin.

8.1.9 Availability / How Supplied

Tamoxifen is commercially available in 10 mg and 20 mg tablets.

8.1.10 Side Effects

1. Hematologic: Thrombocytopenia, usually mild and transient, leukopenia, anemia.
2. Dermatologic: Rash, erythema.

3. Gastrointestinal: Nausea, vomiting, anorexia (may lead to weight loss), diarrhea or constipation, distaste for food.
4. Genitourinary: Vaginal bleeding or discharge, menstrual changes (amenorrhea, menstrual irregularities), pruritus vulvae.
5. Hepatic: Increased liver enzymes, cholestasis, increased bilirubin, and fatty changes in the liver.
6. Neurologic: Depression, dizziness, lightheadedness, headache, confusion, lassitude, and syncope.
7. Cardiovascular: Hot flashes, thrombophlebitis, thromboembolism, pulmonary embolism, fluid retention and edema. Thrombotic events, DVT, clotting factor abnormalities.
8. Ocular: Retinopathy, corneal opacity, slight increased risk of cataracts; corneal scarring and retinal changes have been reported.
9. Metabolic: Hypercalcemia.
10. Other: Tumor "flare" may occur in the first month of therapy, manifested as an increase in tumor-related symptoms, such as bone pain, increase in tumor size, erythema. Weight gain, fluid retention, and edema.
11. Effects in pregnancy: classified as Category D; women should not become pregnant while taking tamoxifen.
12. Secondary cancers: Tamoxifen increases the risk for uterine cancer and the possibility of death from this disease. Patients receiving tamoxifen should have routine gynecologic exams and report any menstrual irregularities, abnormal vaginal bleeding, changes in vaginal discharge and/or pelvic pain or pressure. Tamoxifen may possibly increase the risk for gastrointestinal cancers.

8.1.11 Nursing/Patient Implications

1. Monitor carefully for tumor flare reactions.
2. Teach patients and families to recognize signs and symptoms of hypercalcemia.
3. Advise patient of potential vaginal bleeding and menstrual changes, hot flashes.
4. Teach patients and families to recognize the signs and symptoms of thromboembolic events, namely deep vein thrombosis (DVT) and pulmonary embolism (PE).

NOTE: A patient medication diary is available in [Appendix IV](#) to monitor tamoxifen administration.

8.1.12 References

- Legha SS. Tamoxifen in the treatment of breast cancer. Ann Intern Med 1988; 109:219-228.
- Love RR. Tamoxifen therapy in primary breast cancer: Biology, efficacy and side effects. J Clin Oncol 1989; 7:803-815.
- Please see tamoxifen package insert for more information.

9. Statistical Considerations

The primary purpose of this study is to evaluate whether patients with blood samples with CYP2D6 score of 0 (poor metabolizer) have a reduced progression-free survival (PFS) relative to patients with samples with a CYP2D6 score of 1 or 2 (intermediate and extensive metabolizers, respectively). A total of 240 patients will be enrolled in this study. Assuming a monthly accrual of 10 patients, 24 months of accrual is needed. The below calculations assume that 85% (204/240) of the patients enrolled have samples where a CYP2D6 score of 0, 1, or 2 can be assigned.

CYP2D6 SCORING

We will use a scoring system that has been recently modified from Gaedigk et al (18) to include known CYP2D6 variants and inhibitors:

CYP2D6 Allele	Points Assigned/Alele
*1, *1xN, *2, *2xN, *35	1
*9, *10, *17, *41	0.5
*3, *4, *5, *6, *11	0
Medication	Points Adjustment
Paroxetine, Fluoxetine, Bupropion	-2
Sertraline, Duloxetine, Citalopram, Escitalopram, Celecoxib, Diphenhydramine, Chlorpheniramine	-1
Venlafaxine	-0

An overall comparison of patients with scores CYP2D6=0 vs. CYP2D6= 1 or 2 with respect to progression-free survival will be made. It is estimated that approximately 10% will have a score=0, 40% with a score=1 and 50% with a score=2. A hazard ratio (HR) greater than 1.95 or 2 is of interest to influence change in practice. The table below shows the HRs that can be detected with 80% power when all patients have been followed at least 3 months and disease in 180/204 (88%) has progressed. A log-rank test with a 2-sided 5% type I error rate will be used for the comparison.

Hazard Ratios that can be detected with 80% power

Prevalence of patients with CYP2D6 Score=0				
8%		10%		12%
2.09		1.95		1.86

For example, if 10% of the patients have samples with a CYP2D6 score=0, there is 80% power to detect a hazard ratio of 1.95 (comparing score=0 to score=1 or 2).

Due to the disproportionate expected percentage of poor vs. intermediate and extensive metabolizers, Cox proportional hazards models will be used to estimate the effect of CYP2D6 score with respect to PFS while adjusting for possible confounding factors such as prior AI use and other biomarkers that are being assessed in this study, to assess the

effect of prior AI use and other biomarkers alone with respect to PFS, and to test for interactions between the various baseline factors with respect to PFS.

Due to the low estimated percentage of patients with a CYP2D6 score =0, a stopping rule is incorporated into this design. If the rate of accrual of poor metabolizers is less than 8% or less than 1 patient with a CYP2D6 score=0 per month in the first 18 months that the study is open, the study will be suspended for further evaluation of feasibility.

The distribution of progression-free survival for the patients with a CYP2D6 score=0, 1, and 2 will be estimated using the Kaplan Meier method. Best overall response rate will be summarized as a proportion overall and within patients with a CYP2D6 score=0 vs. 1+2 and within score=0, 1, and 2. Proportion progression-free at 6 months will be summarized overall and within patients with CYP2D6 score=0 vs. 1+2, and within score=0, 1, and 2. Endoxifen levels will be summarized descriptively overall and within responders and non-responders. Comparisons between responders and non-responders with respect to endoxifen levels will be explored using a Wilcoxon rank sum test.

Safety Monitoring

Interim analyses of toxicity are performed twice yearly for all ECOG-ACRIN studies. Reports of these analyses are sent to the ECOG-ACRIN Principal Investigator or Senior Investigator at the participating institutions. Expedited reporting of certain adverse events is required, as described in Section [5.2](#).

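### Does Section 9 need to say which medication record sets the CYP2D6 score, and whether the assumed shares include the deductions?

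*Combined protocol and SAP*

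**What the plan says.** Section 9 defines the score once. Each allele carries 1, 0.5 or 0 points, and a medication table then lowers the total. The system is described as modified "to include known CYP2D6 variants and inhibitors". Three drugs cost 2 points, venlafaxine costs nothing, and these cost 1 point: "Sertraline, Duloxetine, Citalopram, Escitalopram, Celecoxib, Diphenhydramine, Chlorpheniramine".

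The assumed distribution comes straight after that table: "It is estimated that approximately 10% will have a score=0, 40% with a score=1 and 50% with a score=2". Elsewhere Section 9 ties the score to the specimen. It speaks of "patients with blood samples with CYP2D6 score of 0 (poor metabolizer" and assumes that "85% (204/240) of the patients enrolled have samples where a CYP2D6 score of 0, 1, or 2 can be assigned". The feasibility rule suspends the study for review if the score-0 share is below 8%, or if there is "less than 1 patient with a CYP2D6 score=0 per month in the first 18 months that the study is open".

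Sections 3.1.13 and 5.4 bar the three 2-point drugs before registration and on study. They bar none of the 1-point drugs. The Section 7.1 calendar records concomitant medication before registration, at the end of cycles 1, 2 and 3, every three cycles after that, and off treatment until first progression. The diary in Appendix IV also lists other drugs. Neither record is linked to the score.

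**The concern.** The primary comparison is not randomized, and the score is the exposure. A patient with an allele score of 1 (assumed 40% of patients) who takes a 1-point drug moves to score 0, the small group on which power depends. Three things are unstated: which record counts, at what date, and whether the shares, the 8-12% prevalence table and the feasibility rule are before or after deductions. Section 1.2 adds to the doubt, because its background speaks of poor metabolizers and of gene variants in terms of genotype alone.

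Two harms could follow. The feasibility rule could give different answers on different counting bases. And if a drug started at any time before progression were counted in fixed groups, progression-free time before the start would be credited to score 0, pulling the hazard ratio towards 1.

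**Working it through.** **1. The plan's own table.** Inputs from Section 9: 204 scored patients, 180 progressions, 24 months of uniform accrual, 3 months' minimum follow-up, two-sided 5% log-rank, 80% power. With exponential PFS, split the 180 events into e1 (score 0) and e0 (score 1 or 2), and solve ln(HR) = (1.96 + 0.842) × √(1/e1 + 1/e0).

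- At a 10% share, e1 = 19.6 and e0 = 160.4, so HR = exp(2.802 × 0.2393) = 1.95.
- At 8% and 12% the same method gives 2.09 and 1.86.

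All three match the plan.

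**2. Effect of the basis on power, score fixed at entry.** The documents give no rate of 1-point drug use. Let x be the share of patients on such a drug at registration (an assumption), independent of genotype.

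| Reading | Score-0 share analysed | Detectable HR, 80% power |
|---|---|---|
| Shares already include deductions | 10% | 1.95 |
| Shares are genotype only, deductions added: 10% + 40%·x, x = 5/10/20% | 12/14/18% | 1.86/1.79/1.70 |
| Shares include deductions but the analysis uses genotype only, x = 10% | 6.2% | 2.29 |

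The first two rows use the score as Section 9 defines it, and the plan is met or bettered. The gain in the second row assumes that the drugs act as scored. If they had no effect, the average HR at x = 10% would be exp[(10/14) × ln 1.95] = 1.61. By Schoenfeld's formula, ln(1.61) × √(180 × 0.14 × 0.86) − 1.96 = 0.26, or 60% power. That tests the scoring system, not the choice of record. The third row needs an analysis that drops the medication table.

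**3. Feasibility rule.** The plan says "Assuming a monthly accrual of 10 patients". Expected score-0 accrual is 10 × 0.85 × 0.10 = 0.85 per month, below 1. Over 18 months, 10 × 18 = 180 are enrolled and 180 × 0.85 = 153 scored; fewer than 18 with score 0 triggers the rule. Exact binomial chance of that:

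| Score-0 share counted | 153 scored | all 180 scored |
|---|---|---|
| 6.2% | 99% | 97% |
| 10% | 73% | 46% |
| 12% | 43% | 17% |
| 14% | 18% | 4% |
| 18% | 1% | 0.1% |

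If the shares are genotype only and the rule counts deductions, 8.5 × (0.10 + 0.40x) = 1 gives x = 4.4% as the point where expected accrual reaches 1. If the shares and the rule are both after deductions, the 10% row applies whatever the drug use.

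**4. Drugs started on study.** The cut-off condition "followed at least 3 months and disease in 180/204 (88%) has progressed" implies a median PFS: solve 1 − [exp(−3L) − exp(−27L)]/(24L) = 180/204, which gives 3.55 months. Simulation (4,000 trials per cell): true HR 1.95; assumed 2/5/10% of score-1 patients starting a 1-point drug within 6 months; drugs acting as scored.

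| Drug use counted | Mean HR | Power |
|---|---|---|
| At registration only | 2.00/1.99/1.98 | 80/80/79% |
| To end of cycle 3 | 1.97/1.93/1.86 | 80/79/77% |
| Any time before progression | 1.82/1.63/1.42 | 71/56/38% |

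A re-run of 3,000 trials per cell agreed within simulation error. Only the last row does real damage.

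**5. Which row does the text support?** The score is attached to patients through their blood samples, the feasibility rule counts it as patients accrue, and the Cox paragraph treats the factors as baseline ones. Section 11.1.1 lets the blood be drawn at the end of cycle 3, but inherited genotype does not change, and that allowance says nothing about later drugs. Section 7.1 schedules the medication record without linking it to the score.

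**The case for a change.** The strongest opposing case is that the exposure in a non-randomized study should be fixed in writing before outcomes are seen. Two medication records exist, and the wording about samples sits awkwardly with a score that depends on drugs. Scoring 2-point drugs that are barred at entry might suggest that on-study use was meant to count. A short clarification would be cheap, because pre-study medication is already collected.

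Part of this stands. The omission is real, and the 1-point drugs are permitted, so deductions can reach enrolled patients. The chance of meeting the feasibility rule does differ between counting bases.

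The rest is weaker. Section 1.2 reports how other cohorts labelled their patients and gives background; it does not define this trial's score. The 2-point row may cover non-compliance or be carried over from the source system. The rule leads to a suspension for review, where the counting basis would come up at once. The large losses need either the medication table to be ignored or on-study use to be scored, and the text directs neither. A sentence on the record would document the natural reading without correcting a result. It would also leave half-point and negative scores unmapped, which is a different gap.

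**Conclusion.** No change follows. This is missing detail with a natural reading: genotype points less deductions from the medication record at entry, with the shares, the prevalence table and the feasibility rule on the same basis. Under it the planned detectable HR of 1.95 at a 10% share holds, and simulated power is 79-80% even with 10% of score-1 patients starting a 1-point drug within 6 months. The fall to HR 1.42 and 38% power belongs to a reading that no section supports.

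The drug-use rates are assumptions, taken as independent of genotype, and half-point scores are ignored. The figures therefore show sensitivity and are not estimates. The shortfall of 0.85 score-0 patients per month against a threshold of 1 (73% chance of meeting the rule among 153 scored patients, 46% if all 180 are scored) comes from the plan's stated 10% share. It concerns the feasibility rule itself and should be judged separately.

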1. Introduction

Tamoxifen remains the most common endocrine intervention prescribed to women with all stages of hormone receptor positive breast cancer or to decrease the incidence of the disease. Recent data suggest that genetic variants in the cytochrome P450 2D6 (CYP2D6) gene or inhibition of the enzyme result in altered metabolic profile and reduced efficacy. The overall goal of this clinical trial is to determine whether variants in CYP2D6 influence progression free survival and other outcomes in women with metastatic breast cancer, and to explore the role of other genetic variants.

Hypotheses:

Breast cancer patients with a CYP2D6 score of 0 (poor metabolizers) will have a reduced progression-free survival compared to those with a score of 1 or 2 (intermediate or extensive metabolizers, respectively, Hazard ratio 1.89 for poor metabolizer relative to extensive or intermediate metabolizer based on Mayo Clinic investigators).

Fewer breast cancer patients with a CYP2D6 score of 0 will be progression-free at 6 months compared to those with a score of 1 or with a score of 2. Furthermore, participants with higher endoxifen concentration will have improved time to progression compared to those with lower concentration.

We have observed significant correlation between ESR variants and tamoxifen-induced hot flashes. A correlation between ESR and tamoxifen efficacy has never been tested. We hypothesize that candidate variants in ESR1 and ESR2 may influence time to progression. In addition, other genes that are important in tamoxifen's metabolism have not been well-studied. Candidates include: ESR1 Pvull, ESR1 XbaI, and ESR2-02, UGT, and SULT1A1.

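### The Section 9 scoring table produces totals of -1, -0.5, 0.5 and 1.5, but the primary comparison, the three-level analysis and the feasibility rule name only 0, 1 and 2

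*Combined protocol and SAP*

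**What the plan says.** Section 9 scores each of the two alleles at 1, 0.5 or 0 points. Duplicated alleles also score 1, so genotype alone cannot exceed 2. Medication then adjusts the total: -2 for "Paroxetine, Fluoxetine, Bupropion", -1 for "Sertraline, Duloxetine, Citalopram, Escitalopram, Celecoxib, Diphenhydramine, Chlorpheniramine", and nothing for venlafaxine. Sections 3.1.13 and 5.4 prohibit the three -2 drugs and quinidine, and none of the -1 drugs.

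The analyses use three exact values:

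- Primary (Sections 2.1 and 9): "An overall comparison of patients with scores CYP2D6=0 vs. CYP2D6= 1 or 2 with respect to progression-free survival will be made".
- Three-level (Sections 2.2.1 and 9): "The distribution of progression-free survival for the patients with a CYP2D6 score=0, 1, and 2 will be estimated using the Kaplan Meier method".
- Feasibility rule (Section 9), judged over 18 months from opening, with suspension for review as the consequence: "If the rate of accrual of poor metabolizers is less than 8% or less than 1 patient with a CYP2D6 score=0 per month".

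Two planning statements bear on who is covered. One is the distribution: "It is estimated that approximately 10% will have a score=0, 40% with a score=1 and 50% with a score=2". The other says the calculations "assume that 85% (204/240) of the patients enrolled have samples where a CYP2D6 score of 0, 1, or 2 can be assigned". Section 9 labels scores 0, 1 and 2 as poor, intermediate and extensive metabolizers, and the Section 1 hypothesis does the same for zero: "Breast cancer patients with a CYP2D6 score of 0 (poor metabolizers) will have a reduced progression-free survival".

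**The concern.** The score is the exposure in the primary test, and the plan's own table produces values that its analyses do not mention. Negative totals are the most awkward case. A patient with two null alleles who takes a permitted -1 drug scores -1, the lowest total a compliant patient on at most one such drug can have. Under the wording that patient is not score 0, although the hypothesis is about exactly such patients. Half-point totals are the other case: 0.5 lies between poor and intermediate, and 1.5 between intermediate and extensive.

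Only about 20 patients are expected in the poor group (10% of 204 = 20.4), so the placement of a few patients changes both the contrast and the count that drives the feasibility rule. The study is open-label and several groupings fit the text. If the mapping is not fixed before PFS is analysed, it can be chosen, or appear to have been chosen, with the outcome in view.

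**Working it through.** **Attainable totals.** Inputs are the Section 9 allele points and one -1 adjustment. The -2 drugs are left out because they are prohibited.

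| Allele points | No -1 drug | One -1 drug |
|---|---|---|
| 0 + 0 | 0 | **-1** |
| 0 + 0.5 | **0.5** | **-0.5** |
| 0 + 1 | 1 | 0 |
| 0.5 + 0.5 | 1 | 0 |
| 0.5 + 1 | **1.5** | **0.5** |
| 1 + 1 | 2 | 1 |

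Totals in bold have no named group: 2 of 6 without a drug and 3 of 6 with one, so 5 of 12 combinations. This counts combinations, not patients.

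**The plan's power table.** Inputs from Section 9 are 204 scored patients, 180 events, 24 months' accrual, at least 3 months' follow-up and a two-sided 5% log-rank test. I assume exponential PFS and uniform accrual.

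- Event probability at hazard λ: P(λ) = 1 - (e^(-3λ) - e^(-27λ)) / (24λ).
- With poor share p and hazard ratio h, λ solves N[p·P(λh) + (1-p)·P(λ)] = D. Events are d0 = N·p·P(λh) in the poor group and d1 = N·(1-p)·P(λ) in the rest.
- Power = Φ( ln h / √(1/d0 + 1/d1) - 1.96 ).

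At p = 10% and h = 1.95, d0 = 19.6, d1 = 160.4 and the standard error is √(1/19.6 + 1/160.4) = 0.239. Then 0.668/0.239 - 1.96 = 0.83, giving 79.7% power. At 8% (h = 2.09) power is 79.9%, and at 12% (h = 1.86) it is 80.0%. Solving for 80% power gives hazard ratios of 2.09, 1.95 and 1.86, which are the plan's three figures.

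**What the mapping could do to power at a hazard ratio of 1.95.** The documents give no allele or co-medication frequencies, so the share f with unnamed totals is an assumption.

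| Scenario | Patients / events | Power |
|---|---|---|
| Dropped proportionally, f = 10% | 184 / 162 | 75.4% |
| Dropped proportionally, f = 20% | 163 / 144 | 70.4% |
| Dropped proportionally, f = 30% | 143 / 126 | 64.6% |
| Only non-poor dropped, f = 10 / 20 / 30% | as above, 20.4 poor kept | 79.2 / 78.5 / 77.5% |
| All kept, poor share 6% | 204 / 180 | 60.1% |
| All kept, poor share 8% | 204 / 180 | 71.5% |
| All kept, poor share 12% | 204 / 180 | 85.5% |
| All kept, poor share 15% | 204 / 180 | 91.2% |

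The last four rows hold the hazard ratio at 1.95. In practice, moving the cut-point would also change the true contrast, so they show sensitivity to group size alone.

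**Two further gaps in the same definition.** First, the plan does not say whether two -1 drugs add up. With a cut at <=0 versus >0, adding them moves 2 of the 6 allele pairs into the low group: 0.5 + 1 goes from 0.5 to -0.5, and 1 + 1 goes from 1 to 0. Second, no time is given at which drug use is scored, while Section 7.1 records medication up to first progression. Progression at the end of cycle 3 gives 4 records (pre-study and cycles 1, 2 and 3). Progression at the end of cycle 12 gives 7 (adding cycles 6, 9 and 12).

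**The case against.** The strongest reply is that three bins covering everyone were plainly meant. The scores carry the labels poor, intermediate and extensive, and the assumed split is 10 + 40 + 50 = 100%. The -2 adjustment is just large enough to take any genotype to 0 or below, which would fit a floor at zero. This is good evidence of intent, and it makes deliberate exclusion the less likely reading. It does not say where 0.5 or 1.5 belongs, and no floor is stated. The scoring system is described as modified from its cited source, so a mapping in that source cannot be assumed to apply.

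The 85% assumption might also be said to cover unnamed totals. The plan does not say who makes up the other 15%. On that reading the 204 patients and 180 events stand, but these patients are still outside the primary test.

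A reader might infer that group membership will depend on time on study. The documents do not establish this. Section 9 ties the score to blood samples, which are preferably taken before treatment, and it refers to baseline factors. The dependence arises only if any on-study drug use is counted. The record counts measure opportunity, not bias, and patients with long PFS would then drift toward low scores, against the hypothesised effect. Timing is therefore a secondary point.

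A reader might also make much of the -2 row. Those drugs are prohibited, so the totals they produce arise only from deviations.

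**Conclusion.** The definition of the primary exposure is wrong as written. Totals of -1, -0.5, 0.5 and 1.5 can occur in compliant patients and belong to no named group, and the stated rule leaves out of score 0 a patient with two null alleles on a permitted -1 drug. The same gap affects the three-level analysis and the feasibility count.

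The size cannot be fixed from the documents. Under the assumed 10-30% with unnamed totals, the loss at a hazard ratio of 1.95 runs from under 1 percentage point (only non-poor patients dropped, f = 10%: 79.7% to 79.2%) to about 15 points (proportional dropping, f = 30%: 79.7% to 64.6%). If everyone is kept, power depends on the poor share that the cut-point creates: 60% at a 6% share and 91% at 15%.

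Three stronger readings are not supported. The power table is not in error, since it reproduces. The 5 of 12 combinations are not a share of patients. And the plan does not say that it intends to exclude anyone; it omits the rule that would include them.

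**What to change.** In Sections 2 and 9, before PFS is analysed:

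- Set negative totals to 0 and make the primary comparison <=0 versus >0 in all patients with an assignable genotype.
- State cut-points for the three-level analysis, for example <=0, 0.5-1 and 1.5-2. The documents do not settle this choice, so it should be recorded as a decision.
- Pre-specify one sensitivity analysis of <=0.5 versus >0.5.
- Use the same definition in the feasibility rule, and say whether the 10/40/50 split and the 85% figure refer to these groups.
- As a secondary matter, fix one time at which medication is scored, for example the pre-study record, and state whether two -1 drugs add up.

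The cost is mainly wording and these decisions; genotype and concomitant medication are already collected. There are three downsides. Placing 0.5 in the comparison group may dilute the contrast slightly, which the sensitivity analysis would show. Scoring at baseline misses drugs started later. And the documents do not show that the pre-study medication record captures -1 drugs taken over the counter: the Appendix IV diary asks about over-the-counter products but covers treatment cycles only. If baseline scoring is chosen, that capture should be confirmed.
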